5. TRIAL DESIGN

5.1 Overall Design and Plan

This is an open-label, multicenter trial composed of 2 parts in which Pan-HER will be evaluated when administered by IV to patients with advanced epithelial malignancies without available therapeutic options:

- Part 1 is a Phase 1a dose-escalation evaluating Q1W and Q2W schedules of administration in separate dose-escalation cohorts to determine the recommended phase 2 dose (RP2D) and regimen of Pan-HER
- Part 2 is a Phase 2a dose-expansion at the RP2D and regimen. Four (4) dose-expansion cohorts will be evaluated in this part of the trial and will be selected based upon findings from Part 1, additional preclinical data, and additional clinical data available at that time from other agents inhibiting these targets. Patients will be entered, depending upon either a defined molecular profile or profiles, or their underlying malignancy, to 1 of 4 corresponding expansion cohorts: Cohort A (HER2+ solid tumor malignancy Basket Cohort), Cohort B (pancreatic carcinoma), Cohort C (TBD), or Cohort D (TBD).

During Part 1, cohorts of patients will receive increasing doses of Pan-HER on either a Q1W or a Q2W schedule until establishment of the following for each schedule:

- A maximum administered dose (MAD), the highest dose level administered (in mg/kg).
- An MTD; a dose level below the MAD, which is evaluated to have a toxicity level of <33%. An MTD may or may not be found within the dose levels tested. Dose-escalation may be stopped due to toxicity observations other than DLTs and/or results from PK and/or target engagement analyses.
- A RP2D; the RP2D may be equal to or lower than the MTD for the Q1W and/or Q2W dosing regimens.

During Part 2, expansion cohorts of patients will receive the RP2D and regimen. The RP2D and regimen ultimately identified for use in this trial may be comprised of a fixed dose and schedule, a combination of doses to be administered on either a Q1W or Q2W schedule, or a combination dose and regimen.

The RP2D and regimen will be selected based on tolerability demonstrated with Q1W and Q2W dosing during Part 1, as well as available PK and target engagement results, as applicable. Doses

Confidential Page 34 of 156

lower than the MTD(s) but between doses investigated in Part 1 may be selected if data indicate them to be optimal.

The Part 1 starting dose of Pan-HER will be 1 mg/kg Q1W. The following dose levels of Pan-HER are planned to be evaluated:

Q1W

Dose Level 1: 1 mg/kg Q1W

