Additional Patients: There is the potential for additional patients to be enrolled in the dose-escalation portion of the trial to ensure a sufficient number of evaluable patients per cohort by entering an additional patient to a cohort (e.g., increase a 1 patient cohort to 2 patients, a 3 patient cohort to 4 patients, or a 6 patient cohort to 7 patients).

Note: Should this action be taken, cohort tolerability assessment and subsequent dose-escalation will occur when the minimum number of patients required to evaluate tolerability have completed Cycle 1. However, if any additional patient experiences an event that would, per protocol, result in either cohort expansion or the halting of dose-escalation, protocol rules as outlined herein will be followed.

Escalation Rules: Escalation from a current dose level to the next will only proceed following evaluation of tolerability of the current dose level. Thus, dosing of the first patient at any new dose level will commence only after all patients to be treated at the current dose level have completed Cycle 1, and the current dose level has been found to be tolerable. The dose-escalation decision points are listed below:

- If no DLTs are encountered in any of the first 3 patients completing Cycle 1 within a dose level, dose-escalation may continue to the next level
- If 1 of 3 patients within a dose level experiences a DLT, 3 more patients will be enrolled at the same dose level (to a total of 6 patients). If no DLTs are encountered in the 3 additional

Confidential Page 58 of 156

patients, dose-escalation may continue to the next level when all patients have completed and tolerated Cycle 1

- If ≥2 patients within a dose level (of up to 6 patients) experience a DLT, then that dose will be considered to have exceeded the MTD and the dose level just below this MAD will be considered to be the potential MTD
- Once the potential MTD has been declared, the MTD dose level will be completed to a total of 6 patients, if not already accomplished. In order to confirm the MTD, ≤1 of 6 patients within a dose level may have experienced a DLT
- An MTD may or may not be found within the dose levels tested. Dose-escalation may be stopped due toxicity observations other than DLTs and/or results from PK and/or target engagement analyses

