10.3 Primary Endpoint and Analysis

10.3.1 Part 1, Dose-Escalation

The primary objective of the dose-escalation part is to assess the safety and tolerability of Pan-HER. This will be assessed by the primary endpoint for Part 1: occurrence of DLTs during Cycle 1 for each of the Pan-HER dose regimens.

All DLT events will be listed by dose cohort and patient. A summary table of DLTs across dose cohorts by System Organ Class (SOC) and preferred term will be presented, if applicable. The summaries will include number of DLTs, number, and percentages of patients experiencing a DLT. The definition of a DLT is included in **Section 9.5.1**.

The MTD is defined as the highest dose with a maximum of 1 out of 6 patients experiencing a DLT. The MTD may or may not be found within the dose levels tested. Based on an overall evaluation of the dose-escalation part, the RP2D to be used in Part 2 will be selected. The RP2D may be equal to or lower than the MTD.

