3 INVESTIGATIONAL PLAN

3.1 Overall Study Design and Plan

This is an open-label, multicenter trial composed of 2 parts in which Pan-HER will be evaluated when administered by the IV route to patients with advanced epithelial malignancies without available therapeutic options:

- Part 1 is a Phase 1a dose-escalation evaluating Q1W and Q2W schedules of administration in separate dose-escalation cohorts to determine the RP2D and regimen of Pan-HER.

PAREXEL International
Statistical Analysis Plan Template for Early Phase Studies

Symphogen A/S
Sym013-01

- During Part 1, cohorts of patients will receive increasing doses of Pan-HER on either Q1W or a Q2W schedule until establishment of the following for each schedule:
 - A maximum administered dose (MAD), the highest dose level administered (in mg/kg).
 - A maximum tolerated dose (MTD), the highest dose of SYM013 with <33% patients who have experienced dose limiting toxicity (DLT) as defined by the protocol during cycle 1 of study treatment. Q1W and Q2W regimens may have different MTDs;
 - A RP2D, determined based safety of Q1W and Q2W dose regimens as well as available PK and target engagement results, was to be identified. The RP2D may be equal to or lower than the MTD for the Q1W and/or Q2W dosing regimens.

The Part 1 starting dose of Pan-HER will be 1.0 mg/kg Q1W. The following dose levels of Pan-HER are planned to be evaluated:

Q1W

- Dose Level 1: 1 mg/kg Q1W
- Dose Level 2: 2 mg/kg Q1W
- Dose Level 3: 4 mg/kg Q1W
- *Dose Level 4P: 6 mg/kg Q1W + P (lower doses with prophylaxis may be explored, if indicated)
- *Dose Level 5P: 9 mg/kg Q1W + P
- *Dose Level 6P: 12 mg/kg Q1W + P (no patient enrolled in this dose level)
- *Dose Level 7P: 15 mg/kg Q1W + P (no patient enrolled in this dose level)
- *Dose Level 8P: 18 mg/kg Q1W + P (highest potential dose allowed per protocol) (no patient enrolled in this dose level)

PAREXEL International
Statistical Analysis Plan Template for Early Phase Studies

Symphogen A/S

Sym013-01

Q2W

- Dose Level 4: 6 mg/kg Q2W
- Dose Level 5: 9 mg/kg Q2W
- *Dose Level 5P: 9 mg/kg Q2W+ P
- *Dose Level 6P: 12 mg/kg Q2W+ P
- *Dose Level 7P: 15 mg/kg Q2W + P
- *Dose Level 8P: 18 mg/kg Q2W + P (highest potential dose allowed per protocol) (no patient enrolled in this dose level)

*Mandatory intensive IRR and oropharyngeal mucositis prophylaxis; 4-hour infusion (designated “P”)

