4.5 Analysis Sets

Two analysis sets will be defined in accordance with the consolidated ICH E9 GCP guidelines.

The Full Analysis Set (FAS) will comprise all enrolled patients who have received at least one dose of Pan-HER. The FAS will be used for evaluation of all endpoints except evaluation of DLTs. The patients in the FAS will contribute to the analyses as allocated to treatment (patients will be reported below the regimen and dosage actually received). For the evaluation of PK endpoints, patients, full profiles, or single measurements can be excluded from the analyses with justification. The decision of excluding patients, full profiles, or part of profiles will be described in the clinical trial report (CTR).

The DLT Analysis Set will comprise all patients in the FAS enrolled in Part 1, except patients who did not complete Cycle 1 for reasons other than drug toxicity. The DLT Analysis Set will be used for evaluation of DLTs and the MTD or lack thereof.

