4.11 Safety Evaluation

All safety summaries will be based upon the FAS as defined in Section 4.5.

4.11.1 The DLT Analysis Set will be used for evaluation of DLTs Dose Limiting Toxicities (DLT)

All DLT events will be listed. Presence and absence of DLTs will be presented by regimen and dose in the order of date of first dose.

PAREXEL International
Statistical Analysis Plan Template for Early Phase Studies

Symphogen A/S
Sym013-01

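### SAP 3.1 defines the MTD only as fewer than 33% DLTs and drops the protocol's count rule, so 2 of 7, or a cohort never completed to six, can qualify

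*Protocol*

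**What the plan says.** The protocol's statistical definition is a count. Section 10.3.1, repeated in the Synopsis, reads: "The MTD is defined as the highest dose with a maximum of 1 out of 6 patients experiencing a DLT". The decision points in 7.1.3.2 add that two or more patients with a DLT put a level above the MTD, and that a candidate MTD level is filled to six patients, of whom no more than one may have had a DLT.

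Protocol 5.1 instead uses a proportion: "An MTD; a dose level below the MAD, which is evaluated to have a toxicity level of <33" per cent. SAP 3.1 follows that route and gives the MTD as "the highest dose of SYM013 with <33% patients who have experienced dose limiting toxicity". It states no count and no minimum cohort size, and it omits the condition in Protocol 5.1 that the MTD lie below the MAD.

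SAP 4.5 assigns a population to the question: "The DLT Analysis Set will be used for evaluation of DLTs and the MTD or lack thereof". SAP 4.11.1 plans the display: "Presence and absence of DLTs will be presented by regimen and dose in the order of date of first dose". SAP 4.14, which lists changes to the planned analysis, does not mention the MTD.

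Cohort sizes other than three and six are allowed. The Additional Patients paragraph of Protocol 7.1.3.2 lets a cohort of three become four and a cohort of six become seven. Its Note says that "cohort tolerability assessment and subsequent dose-escalation will occur when the minimum number of patients required to evaluate tolerability have completed Cycle 1", and then sends any expansion or halting event in the extra patient back to the protocol's rules.

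**The concern.** A count rule and a percentage rule can be used interchangeably only at the cohort sizes for which the percentage was chosen. At six patients, under 33% and at most one DLT mean the same thing. At seven they do not, and seven is a permitted size. The percentage also says nothing about how many patients must have been observed, so a level abandoned after three or four patients can satisfy it. That matters in a trial whose enrollment stopped during Part 1, because the last levels opened may not have been filled to six.

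At stake is how a dose level is labelled in the report: within the MTD, beyond it, or not established. An analyst working from the SAP alone could reach a different label from one applying Protocol 10.3.1, and nothing in the SAP says which prevails.

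**Working it through.** **Inputs.** SAP 3.1: under 33%. Protocol 10.3.1 and 7.1.3.2: at most 1 of 6, two or more exceeds, filled to six. Protocol 7.1.3.2: cohorts of 4 and 7 allowed. Protocol 3.2.4.1: seven patients entered at 9 mg/kg Q2W, with two events meeting DLT criteria.

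**1. The protocol's own threshold.** 1/6 = 16.7% passes both rules. 2/6 = 33.3% fails both. At six patients the definitions agree.

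**2. Other sizes.**

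| DLTs / evaluable | Proportion | SAP 3.1 (<33%) | Protocol count rule |
|---|---|---|---|
| 0/3 | 0% | qualifies | may escalate, but not an MTD until filled to 6 |
| 1/4 | 25.0% | qualifies | cohort must be expanded; not yet an MTD |
| 1/6 | 16.7% | qualifies | qualifies |
| 2/6 | 33.3% | fails | exceeds the MTD |
| 2/7 | 28.6% | qualifies | exceeds the MTD |

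Two DLTs pass the percentage when 2/n < 0.33, that is n > 6.06, so seven is the smallest cohort at which the rules part on two DLTs.

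**3. The cohort that occurred.** Protocol 3.2.4.1 describes two DLTs at 9 mg/kg Q2W: a Grade 3 infusion-related reaction in a patient who was discontinued, and Grade 3 oropharyngeal mucositis in a patient later retreated at a lower dose. These are different patients. The DLT Analysis Set removes only those who missed completing Cycle 1 for reasons other than drug toxicity, so neither DLT should drop out of the numerator. With seven evaluable, 2/7 = 28.6% (exact 95% CI 3.7% to 71.0%), and the rules disagree. If one DLT-free patient is not evaluable, 2/6 = 33.3% and they agree. The documents do not give the evaluable number.

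**4. How often a cohort of seven would split the rules.** The rules disagree at exactly 2 of 7, with probability 21p²(1−p)⁵. Independence and the true rates p are assumptions for illustration.

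| p | Exactly 2 of 7 | Accepted by count rule, P(≤1 of 7) | Accepted by <33%, P(≤2 of 7) |
|---|---|---|---|
| 0.20 | 0.275 | 0.577 | 0.852 |
| 0.25 | 0.311 | 0.445 | 0.756 |
| 0.33 | 0.309 | 0.270 | 0.578 |
| 0.40 | 0.261 | 0.159 | 0.420 |

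Three of the 21 arrangements put both DLTs in the first three patients, which would halt the level at once. Leaving them out gives 18p²(1−p)⁵ = 0.236, 0.267, 0.265 and 0.224. All of these are conditional on seven evaluable patients. They compare two readings and do not estimate this drug's toxicity.

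**5. Whether that cohort can set the Q2W MTD.** Among the Q2W levels, SAP 3.1 marks only 18 mg/kg as having no patient. SAP 4.10.4.1 plans a PK panel for 12 mg/kg Q2W with prophylaxis. So 12 mg/kg was opened, and under Protocol 7.1.3.2 that required 9 mg/kg Q2W with prophylaxis to have been found tolerable. The highest qualifying level should therefore be 9 mg/kg with prophylaxis or above under the SAP wording. DLT counts for those levels are not in the documents.

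**The case against.** The best case against the point is that SAP 3.1 only recaps the design. It repeats a threshold already in Protocol 5.1, keeps a standard 3+3 for escalation, and declares no intention to replace Protocol 10.3.1. No listed output derives an MTD, enrollment has stopped, and a reader given n and the DLT count per level can apply either rule. Most of this stands and is why the point is small. It does not remove the gap: SAP 4.5 says the DLT set serves the MTD evaluation, SAP 3.1 holds the only criterion in the SAP, and its reference to the protocol's definition attaches to the DLT and not to the MTD.

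It can also be said that the protocol's two-DLT bullet is written for up to six patients and so does not reach a seventh. The Note answers this by returning a halting event in the extra patient to the protocol's rules, and 10.3.1 does not accept two DLTs.

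Two stronger readings are tempting. First, a reader might infer that the SAP will misreport the Q2W MTD. The documents do not support that, for the reason in step 5 and because the evaluable number is unknown. Second, a reader might infer that 7.1.3.2 contradicts itself on when the next level may open, because the Note relies on the minimum number of patients while the Escalation Rules allow dosing "only after all patients to be treated at the current dose level have completed Cycle 1". The Note applies only when an extra patient has been added, so it reads naturally as the specific rule for that case. The first decision point, which looks at "any of the first 3 patients completing Cycle 1 within a dose level", fits that reading, and the Note's next sentence deals with a DLT in the extra patient. No level is shown to have opened with a patient still in Cycle 1.

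**Conclusion.** The inconsistency is real and minor. SAP 3.1, following Protocol 5.1, states a weaker MTD rule than Protocol 10.3.1 and 7.1.3.2, and SAP 4.14 does not declare the difference. The rules agree at six patients. They disagree at 2 of 7 and wherever a level was never filled to six.

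The 9 mg/kg Q2W cohort without mandatory prophylaxis is labelled differently by the two rules only if all seven patients are evaluable, and even then it is unlikely to decide the Q2W MTD. The remaining exposure is at the higher levels, where the SAP wording would also apply and where neither DLT counts nor cohort sizes are given. The step 5 inference assumes that the escalation rule was followed.

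**What to change.** In SAP 3.1, and in Protocol 5.1 for consistency, replace the percentage with:

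*MTD: the highest dose level with at least 6 evaluable patients and no more than 1 with a Cycle 1 DLT. Two or more DLTs, including 2 of 7, exceeds the MTD. If no level qualifies, report that no MTD was established.*

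In Table 14.2.4.8, already flagged for the abbreviated report, show the number of evaluable patients at each level and its status under the count rule: qualifies, exceeds, or not filled to six. SAP 4.2 already plans n and percentages, so the addition is mainly the status column.

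The cost is one definition in two places and a small change to one table. No new data or analysis is needed.

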7.1.3.3 Part 2, Dose-Expansion Cohorts

Once the RP2D and regimen have been established during dose-escalation, enrollment into the 4 separate dose-expansion cohorts will commence (Cohort A, Cohort B, Cohort C, or Cohort D). All patients enrolled will be treated with Pan-HER at the established RP2D and regimen.

Confidential Page 59 of 156

7.1.3.4 Duration of Infusion for Administration of Pan-HER

Pan-HER will be administered following delivery of premedication as specified in **Section 7.2.1** and **Section 7.2.2**.

Prior to Amendment 5

As the risk of an IRR is highest for the first administration of a mAb and diminishes with subsequent infusions, the minimum duration of the infusion is required to be approximately 2 hours (+10 minutes) for the first infusion of Pan-HER, approximately 1.5 hours (+10 minutes) for the second infusion and approximately 1 hour (+10 minutes) for all subsequent infusions.

For the first infusion, the infusion rate will start at 1 mL/minute. The infusion rate will be increased at reasonable intervals throughout the 2-hour infusion period according to the trial site practices for IV infusion of mAbs. For subsequent infusions, the infusion rate will be adjusted in order to reach an infusion time of 1.5 and 1 hour respectively.

Recommended guidelines for infusion rates are provided in **Table 5**, **Table 6**, and **Table 7**.

Table 5 Infusion Rate for First Infusion of Pan-HER

Infusion Time Interval	Infusion Rate	Approximate Volume Infused during interval
0-30 min	1 mL/min = 60 mL/h	30 mL
31-60 min	1.5 mL/min = 90 mL/h	45 mL
61-90 min	2 mL/min = 120 mL/h	60 mL
91- approx. 120 min	4 mL/min = 240 mL/h	115 mL
		Total = 250 mL

Abbreviations (in alphabetical order): h, hour; min, minutes

Table 6 Infusion Rate for Second Infusion of Pan-HER

Infusion Time Interval	Infusion Rate	Approximate Volume Infused during interval
0-30 min	1 mL/min = 60 mL/h	30 mL
31-60 min	2.5 mL/min = 150 mL/h	75 mL
61- approx. 90 min	5 mL/min = 300 mL/h	145 mL
		Total = 250 mL

Abbreviations (in alphabetical order): h, hour; min, minutes

Confidential Page 60 of 156

Table 7	Infusion Rate for	Third and Subsec	quent Infusions	of Pan-HER
---------	-------------------	------------------	-----------------	------------

Infusion Time Interval	Infusion Rate	Approximate Volume Infused during interval
0-30 min	2.5 mL/min = 150 mL/h	75 mL
31- approx. 60 min	5.8 mL/min =350 mL/h	175 mL
		Total = 250 mL

Abbreviations (in alphabetical order): h, hour; min, minutes

The duration of Pan-HER-infusion will be prolonged by 0.5 hours (or longer, if indicated) for all subsequent patients entered to the trial in the following situations:

- In the event of a Grade 2 IRR in \geq two thirds of the patients entered to a cohort
- In the event of a Grade 3 or greater IRR in any patient within a cohort

These same criteria will be applied in the event IRRs occur on an extended infusion schedule.

Amendment 5 Note: Prolongation of Pan-HER infusions by 0.5 hours was implemented on 2 occasions:

- Beginning with Dose Level 5 (9 mg/kg Q2W), and due to Grade 2 IRRs in ≥ two thirds of patients entered to Dose Level 4 (6 mg/kg Q2W), the minimum duration of infusion was prolonged by 0.5 hours to approximately 2.5 hours (+10 min) for the first infusion of Pan-HER, approximately 2 hours (+10 min) for the second infusion, and approximately 1.5 hours (+10 min) for all subsequent infusions.
- During Dose Level 5 (9 mg/kg Q2W), and due to a Grade 3 IRR in a patient entered to Dose Level 5 (9 mg/kg Q2W), the minimum duration of infusion was prolonged by 0.5 hours to approximately 3 hours (+10 min) for the first infusion of Pan-HER, approximately 2.5 hours (+10 min) for the second infusion, and approximately 2 hours (+10 min) for all subsequent infusions.

Effective with Amendment 5

Beginning with Dose Level 5P (9 mg/kg Q2W with intensive prophylaxis) and all patients thereafter, the duration of the infusion is required to be at minimum 4 hours (+10 min) for all infusions of Pan-HER (unless further prolongation is required for an individual patient due to the occurrence of an IRR). Titrated rate increases during infusions, and infusion duration reductions after C1/D1, will no longer be allowed.

Recommendations for management of an IRR in individual patients can be found in **Section 7.1.3.7**.

7.1.3.5 Patient Monitoring During and After Infusion of Pan-HER

Patients will be treated on an outpatient basis.

Confidential Page 61 of 156

Pan-HER infusions must be administered under the close supervision of an experienced physician in an environment where full resuscitation facilities are immediately available.

Patients will be carefully observed for a minimum of 2 hours following completion of the first administration of Pan-HER and a minimum of 1 hour following completion of subsequent administrations. At the end of each infusion, the IV line must remain in place for at least 1 hour to allow administration of IV drugs, if necessary.

7.1.3.6 Infusion-Related Reactions to Pan-HER

An IRR is defined as an AE occurring during the Pan-HER infusion and up to 2 hours after the end of infusion (EOI), which is assessed by the Investigator as possibly, probably, or related to Pan-HER. Signs of IRRs may include but are not limited to facial flushing and swelling, shortness of breath, headache, diaphoresis, tachycardia, hypotension, chills, rigors, chest and throat tightness, as well as chest, back and/or abdominal discomfort.

7.1.3.7 Handling of Infusion-Related Reactions to Pan-HER

Recommended guidelines for management of IRRs are shown in **Table 8**. In all cases, the Investigator should use best clinical judgment in managing such reactions.

Confidential Page 62 of 156

Table 8 Infusion-Related Reactions Management Guidelines

CTCAE Grade	Management/Treatment
Grade 1	Continue infusion; consider slowing to 50% of the prior rate
Mild transient reaction;	Monitor closely
infusion interruption not indicated; intervention not indicated	If infusion is extended, administer subsequent infusions during Cycle 1 at the prolonged rate
	Thereafter, if vital signs remain stable and symptoms do not recur, at the discretion of the Investigator an attempt may be made to slowly increase the rate of infusion. Final infusion duration should not be briefer than the initial rate attempted in the patient
Grade 2	Interrupt infusion for a minimum of 30 minutes
Therapy or infusion interruption indicated but responds promptly to symptomatic treatment (e.g., antihistamines, NSAIDs, narcotics, IV	Administer symptomatic treatment (e.g., antihistamines, NSAIDs, etc.) and appropriate supportive care (e.g., bronchodilator, oxygen, etc.), as indicated
fluids); prophylactic medications indicated for ≤ 24 h	• When symptoms have resolved or decreased to Grade 1, restart infusion at 50% of the prior rate
	Monitor closely
	If symptoms recur, stop the infusion, institute remedial therapy, monitor closely and evaluate whether the patient can continue the trial
	Administer subsequent infusions during Cycle 1 at the prolonged rate
	Thereafter, if vital signs remain stable and symptoms do not recur, at the discretion of the Investigator an attempt may be made to slowly increase the rate of infusion. Final infusion duration should not be briefer than the initial rate attempted in the patient
Grade 3	Discontinue the infusion
Prolonged (e.g., not rapidly responsive to symptomatic medication and/or brief interruption of infusion); recurrence of symptoms following initial improvement;	Administer symptomatic treatment (e.g., antihistamines, NSAIDs, glucocorticoid etc.) and appropriate supportive care (e.g., bronchodilator, oxygen, IV fluid etc.), as indicated
hospitalization indicated for clinical sequelae	Do not resume infusion
	Patient will either be discontinued from further treatment or receive subsequent treatments at a reduced dose (if >6 hours in duration); if treatment is continued administer subsequent infusions during Cycle 1 at 50% of the prior rate
	Thereafter, if vital signs remain stable and symptoms do not recur, at the discretion of the Investigator an attempt may be made to slowly increase the rate of infusion. Final infusion duration should not be briefer than the initial rate attempted in the patient.
Grade 4	Discontinue infusion
Life-threatening consequences; urgent intervention indicated	 Administer necessary life-support measures, as indicated Discontinue from further treatment
	Discontinue from further treatment

Abbreviations (in alphabetical order): CTCAE, Common Terminology Criteria for Adverse Events v4.03; h, hours; IV, intravenous; ; NSAID, nonsteroidal anti-inflammatory drug

Confidential Page 63 of 156

